#### **e) Effectiveness**

Quality-adjusted life years (QALY) over a 4-year period calculated by validated utility-weighting ([www.cearegistry.com](http://www.cearegistry.com)).

## Core Lab DICOM Reads

Participating sites will be asked to provide DICOM images for a random sample of trial-eligible CMR studies (10% of eligible cases at the site). The core lab will review rest perfusion, stress perfusion, and LGE images. The purpose of the DICOM reads is to assess the quality of images and not to dispute the site's interpretation of cases.

DICOM images read by the core lab will be shared with the vendors (Siemens and Bayer).

## Number of Sites

It is expected that a range of 6-15 US centers will participate. Each site will be screened by a sample survey and is required to provide a limited dataset to verify the existence of the stress CMR studies, completeness of key pulse sequences (cardiac function, stress perfusion, and LGE imaging), and diagnostic quality for ischemia assessment. To qualify for the study, a site needs to demonstrate:

- a) Willingness/ability to provide a screening dataset
- b) Can contribute at least 100 studies
- c) <10% of the consecutive cohort were deemed diagnostic inadequate by the site

## Sample Size

### For sub-aim 1:

The rate of cardiac hard events (death and acute MI) is estimated based on reported evidence of 0.5% and 6% per year for patients who have absence and presence of ischemia on CMR perfusion imaging, respectively. We plan to collect follow-up events for a 4-year period after CMR. Based on prior evidence, prevalence of ischemia on CMR perfusion was 23% in referred patients.

With a sample size of 2,200 patients, 506 (23%) are assumed to be with presence of ischemia and 1694 (77%) with absence of ischemia. With incidences of 6% and 0.5% per year and a 4-year follow-up, a total of 124 of 506 patients with ischemia and 36 of 1694 patients with no ischemia are expected to experience an event, i.e. a total of 150 patients with event.

A sample size of 2,200 patients overall and 150 patients with event in a 4-year follow-up is regarded sufficient to run multivariable analysis with up to 10 variables.

With regards to the sample size considerations on the time-to-event analysis, the following settings and assumptions were used:

- Power = 80%
- Level of significance (two-sided) = 5%
- Assumed proportion in control group (i.e. no revascularization) = 77%
- Total sample size = 2,200 patients
- Number of events = 150 in total sample
- 4-year follow-up for all patients available
- The hazard ratio is estimated by a Cox proportional hazard model

With a sample size of 2,200 patients and an event rate of 124 in group 1 and 36 in group 2, a hazard ratio of 0.59 can be detected with the above mentioned settings and assumptions (i.e. 41% risk reduction rate).

For sub-aim 2.3 (comparison to the historical FAME 2 study

As reported in published data (own BWH dataset and [name] et al Circulation 2011 Apr 12;123(14):1509-18), the event rate of patients who underwent revascularization guided by CMR ischemia (i.e. CMR physiologic guidance) is about 5% per year, i.e. 10% in a 2-year follow-up. In the

historic fame-2 study, the 2-year event rate of patients who did not use physiological guidance (N=441), was 19.5%. With a power of 80%, a two-sided alpha of 5% and an assumed difference under H1 of -9.5%, the sample size of patients in this registry needs to be at least 180 patients.

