## Study Endpoints and Hypotheses to Test

### Study Endpoints

Primary outcomes include all-cause mortality, acute myocardial infarction (AMI), and late coronary revascularization (PCI or CABG beyond 60 days after CMR).

Secondary outcomes include non-fatal cardiac events (including cardiac hospitalizations for unstable angina or heart failure, heart transplant, significant ventricular arrhythmias, and strokes), alteration of diagnostic and therapeutic decision, and cardiac event-weighted QALY.

The specific aims of this project are listed below:

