### **Specific Aim 2 – Assessment of the impact of CMR-guided invasive coronary revascularization, compared with medical therapy, on primary outcomes**

Sub-aim 2.1 Using a propensity score-matching analysis, test the hypothesis that in real-world clinical practice that stress CMR perfusion imaging-guided use of invasive coronary revascularization (INT) (defined by INT performed within 60 days after CMR) offers *AMI-free, coronary revascularization-free, survival benefits* over medical therapy (MED) in patients with suspected ischemia. We will estimate the # lives saved per 100 patients treated with INT versus MED (based on predicted primary outcome rate amongst MED)–(predicted primary outcome rate amongst INT)

Sub-aim 2.2 Using a propensity score-matching analysis, test the hypothesis that in real-world clinical practice that stress CMR perfusion imaging-guided use of INT offers *survival benefits free of primary or secondary outcomes* over MED in patients with suspected ischemia.

Sub-aim 2.3 The preferred initial treatment for patients with stable ischemic heart disease (SIHD) is the best available medical therapy. The benefits of using physiologic ischemia-based guidance to performing INT has been shown in the FAME and FAME-2 trials where fraction-flow-reserve was used to assess physiological significance of coronary stenosis. In FAME (multi-vessel SIHD) and FAME 2 (single or multi-vessel SIHD) trials: a 29% and 66% relative risk reduction of primary outcome at 2-years were reported, respectively. CMR perfusion assessment had demonstrated remarkable correlation to FFR based assessment of coronary physiologic significance. For sub-aim 2.3, test the hypothesis that comparing to the FAME-2 primary outcome rate of patients managed by medical management alone, CMR-guided INT patients have a relative risk reduction of 2-year primary outcomes  $\geq 30\%$ .

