#### **c) Clinical Outcomes within 4 years after CMR**

Primary outcomes: a) All-cause including cardiac mortality, b) new acute MI, within 4 years after CMR imaging, and c) late coronary revascularization (PCI or CABG beyond 60 days after CMR);

Secondary outcomes: heart failure hospitalization, unstable angina hospitalization, heart transplantation, significant ventricular arrhythmias, and strokes, within 4 years after CMR. Times to all of the above events will be collected. Other supportive data: angiographic reports including PCI details, CABG operative reports. Repeat events of all non-fatal outcomes will be collected using our web-based data structures (Appendix A4).

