## **Statistical Analyses**

### **Specific aim 1**

Unadjusted and multivariable survival analyses associating presence of ischemia and percent ischemic myocardium (both by CMR), with the primary and secondary clinical outcomes will be performed. In the multi-variable analyses, key known risk markers such as age, patient sex, left ventricular and systolic volume (LVESV), validated pretest coronary disease probability, and validated risk score (Diamond and Forrester) will be modeled, and then extent of ischemia by stress CMR studies will be added to the model to test the null hypothesis that CMR findings do not add predictive value, versus the alternative hypothesis that stress CMR findings do add predictive value. A significance level of 0.05 will be used. Since CMR findings will affect patient management, which in turn, will affect the clinical outcomes, in a secondary analysis, cardiac treatment (e.g. revascularization) received within 60 days of the CMR will be added to the above model to account for treatment effects on the relationship between extent of ischemia and outcome. Annualized event rates of the primary and secondary outcomes, stratified by CMR ischemia (present or absent), and CMR ischemic burden (mild, moderate, high), will be determined, both unadjusted and adjusted for cardiac treatments received. We also plan to calculate net reclassification index of these CMR metrics to event-free survival (primary and secondary outcomes). In addition, we will examine the annual event rates of primary and secondary outcomes in each of these subgroups and perform corresponding comparative analyses.

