**Step 2: Multivariable survival analyses for treatment's impact incorporating the propensity score (sub-aims 2.1 and 2.2).** A Cox proportional hazards model will be used to assess the association of treatment with the primary outcome (sub-aim 2.1) and secondary outcome-free survival (sub-aim 2.2). For each of sub-aim 2.1 and 2.2, we plan to build a survival model using Cox proportional hazards regression to control for the effects of baseline patient differences. Key known risk markers to be included in these models are age, sex, diabetes, and % ischemic myocardium. Major Treatment (INT or MED) and the propensity score will then be entered into the model to assess for any survival advantage from INT vs MED adjusting for the nonrandomized referral pattern. Any potential impact by any covariate in the model onto the survival benefit from INT, will be tested by adding an interaction term between treatment and the covariate of interest.

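### Expected events and the detectable hazard ratio are given for death or AMI only, while the primary outcome also includes late revascularization; no combined death/AMI analysis is named.

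*Combined protocol and SAP*

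**What the plan says.** **Power calculation.** The Sample Size section, in its part on sub-aim 1, states: "The rate of cardiac hard events (death and acute MI) is estimated based on reported evidence of 0.5% and 6% per year", taking the lower figure for patients without ischemia and the higher for those with it. With 1,694 and 506 such patients and four years of follow-up, the section expects 36 and 124 events and gives the total as 150. At 80% power, two-sided 5% and 77% in the control group, it states a detectable HR of 0.59.

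**Primary outcome.** Study Endpoints: "Primary outcomes include all-cause mortality, acute myocardial infarction (AMI), and late coronary revascularization (PCI or CABG beyond 60 days after CMR"). The list of outcomes to collect repeats the third component: "c) late coronary revascularization (PCI or CABG beyond 60 days after CMR").

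**Planned analyses.**
- Aim 1: survival analyses of ischemia "with the primary and secondary clinical outcomes will be performed".
- Sub-aim 2.1: the hypothesis is that early revascularization (INT) offers "AMI-free, coronary revascularization-free, survival benefits" over medical therapy (MED). The number of lives saved per 100 patients treated is to be the difference between MED and INT in predicted primary outcome rates.
- Specific aim 2, Step 2: a Cox model is to "assess the association of treatment with the primary outcome (sub-aim 2.1) and secondary outcome-free survival (sub-aim 2.2").

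**Secondary outcomes.** "Secondary outcomes include non-fatal cardiac events (including cardiac hospitalizations for unstable angina or heart failure, heart transplant, significant ventricular arrhythmias, and strokes"), together with changed diagnostic and therapeutic decisions and QALYs. Death or AMI combined is not among them. Hard events are mentioned only in the Sample Size section.

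**The concern.** A detectable effect belongs to one endpoint and one comparison. Here the event rates, the counts and the HR belong to death or AMI, but the outcome tested has a third component. Its frequency is not stated, and its relation to ischemia or treatment may differ from that of death and AMI.

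Two things are at stake. First, the reader cannot tell what effect on the primary outcome the study can detect. Second, late revascularization is a clinical decision. The plan itself says that CMR findings affect management, and in Aim 2 the same procedure is treatment up to day 60 and an event afterwards. A difference in the primary outcome could therefore come mainly from this component. In sub-aim 2.1 no named analysis would reveal that, and the lives-saved figure would count avoided late procedures as lives.

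**Working it through.** **1. Reproduce the plan's figure.** Inputs from Sample Size: two-sided 5%, 80% power, split 0.77/0.23, so p(1-p) = 0.1771. Schoenfeld's formula for the detectable HR with D events is

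HR = exp(-(1.960 + 0.842) / sqrt(D × 0.1771)).

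- D = 160 (124 + 36): sqrt(28.34) = 5.323; 2.802/5.323 = 0.526; HR = 0.591.
- D = 150 (the stated total): sqrt(26.57) = 5.154; 2.802/5.154 = 0.544; HR = 0.581, with 77.6% power at HR 0.59.

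The stated 0.59 therefore comes from 160 events, all of them death or AMI. Late revascularization contributes nothing to it.

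**2. Compare the endpoints.**

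| Section | Death | AMI | Late revascularization |
|---|---|---|---|
| Sample Size, For sub-aim 1 | yes | yes | no |
| Study Endpoints, primary | yes | yes | yes |
| Data to Collect, c), primary | yes | yes | yes |
| Sub-aim 2.1 and Step 2 | yes | yes | yes |

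**3. Illustrate the primary outcome.** The documents give no late-revascularization rate. Assume r per year in all patients, constant hazards, and only the first event counted:

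D = 506 × [1 - exp(-4(0.06 + r))] + 1,694 × [1 - exp(-4(0.005 + r))].

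| Assumed r | Ischemia | No ischemia | D | Detectable HR (77/23) | Power at HR 0.59 |
|---|---|---|---|---|---|
| 0 | 108.0 | 33.5 | 141.5 | 0.57 | 75% |
| 0.25% | 111.9 | 50.1 | 162 | 0.59 | 81% |
| 2% | 138.6 | 161.2 | 300 | 0.68 | 97% |

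The r = 0 row is the death/AMI count by the same method, so the table compares like with like. It is below the plan's 160 because the plan's 124 and 36 do not follow exactly from its rates: simple multiplication gives 506 × 4 × 0.06 = 121 and 1,694 × 4 × 0.005 = 34.

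**4. Why the HR cannot be assumed constant.** Take r = 2% and suppose, purely for illustration, HR 0.59 for death/AMI and no effect on late revascularization. Among first events, death/AMI accounts for 138.6 × 0.06/0.08 + 161.2 × 0.005/0.025 = 104.0 + 32.2 = 136, or 45% of 300. Weighting the log HR by this share gives approximately exp(0.454 × ln 0.59) = 0.79. Power with 300 events is then Φ(0.240 × sqrt(300 × 0.1771) - 1.960), about 42%. A stronger effect on late revascularization than on death/AMI would move power the other way. The documents do not say which applies.

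**The case against.** **Extra events only help.** At a fixed HR this is correct: power at 0.59 rises from 77.6% with 150 events to 97% with 300. A reader might infer from the mismatch that the study is underpowered; the documents do not support that. For the ischemia contrast in Aim 1, the assumed rates (6% against 0.5% per year) imply an HR near 12, so power is very unlikely to be at risk there. What stands is that 0.59 is not a figure for the primary analysis.

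**Component results may be planned.** The endpoint sections speak of primary outcomes in the plural, the data-collection list letters them a) to c), and Aim 1 plans annualized rates of primary and secondary outcomes. A reader might infer that no planned analysis could separate death and AMI from late procedures. For Aim 1 that goes too far: separate results are possible on this reading, though not clearly specified. For sub-aim 2.1, one combined event-free endpoint is tested and no component analysis is named.

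**The 60-day boundary has a rationale.** Under Specific aim 2 the plan says, from previous work, that referrals after 60 days tended to reflect clinical worsening. That is a fair reason to keep the component, and procedures after day 60 count in INT patients as well. A reader might infer that late revascularization should leave the endpoint; nothing here requires that. A reported tendency does not, however, replace showing death/AMI beside the composite.

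**Conclusion.** The point holds as a mismatch of endpoints. The plan gives expected events and a detectable HR for death/AMI, and neither for the outcome that it tests. Under the assumed 0.25-2% per year, that outcome would have about 162-300 first events and a detectable HR of about 0.59-0.68 at the 77/23 split. These figures rest on the plan's death/AMI rates, an assumed late-revascularization rate equal in both groups, complete four-year follow-up, and no matching or adjustment. They illustrate the dependence on the missing rate and are not a forecast.

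The split is uncertain too. The 77% is the share without ischemia but is labelled as no revascularization, while Specific aim 2 expects 85-90% on MED. The illustration therefore should not be read as the power of sub-aim 2.1.

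The gap in reporting is firm for sub-aim 2.1, including its lives-saved figure. For Aim 1 it is a lack of clear specification.

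**What to change.** (a) Restate expected events and detectable HR for the primary outcome. Give the assumed late-revascularization rate by comparison group, and use the split that belongs to each comparison: ischemia against none for Aim 1, INT against MED for sub-aim 2.1.

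(b) Pre-specify a death/AMI analysis beside the primary outcome for Aims 1 and 2.1, and state that the two are interpreted together. Base any lives-saved figure on mortality. Recompute the detectable HR for death/AMI; the present one cannot be carried over, because 124 + 36 is 160 and not 150, and because its 77% is the no-ischemia share.

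The cost is SAP wording and one extra run of models already planned. No new data are needed: times to all events are to be collected, and the form in Appendix A4 dates death, AMI, PCI and CABG separately. The downside is wider intervals for death/AMI than for the primary outcome.

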### **Specific aim 2 (2 separate analyses for sub-aims 2.1 and 2.2, respectively)**

We structured the present study's analysis of observational data to mimic a randomized clinical trial: a patient's assignment to a treatment was based on the therapy selected in the first 60 days after stress CMR perfusion study and nonrandomized treatment adjusted for via a propensity score. This time point of 60 days was selected from previous work indicating that revascularization performed within this timeframe resulted from the noninvasive imaging study, whereas referrals after 60 days tended to be attributable to worsening clinical status. Based on our pilot data, approximately 10-15% of patients undergo early coronary revascularization within the first 60 days after CMR. We therefore anticipate that 85-90% of the study cohort received MED whereas 10-15% received INT.

We plan to examine the assumptions of proportional hazards in each of the Cox models. In addition, performance of the propensity score model will be tested by comparing the prognostic associations between treatment and clinical outcomes, without and with that propensity score matching. Key risk markers will be compared between the treatment groups, without and with inclusion of the propensity score matching.

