**Step 1: Propensity Score to Treatment** We plan to structure the study analysis of observational data in SA1 to mimic a randomized clinical trial: a) assignment of coronary intervention (INT) vs. medical therapy (MED) is based on the therapy selected in the initial 60 days after imaging and b) nonrandomized treatment adjusted for via a propensity score. Either PCI or CABG will define coronary revascularization. Follow-up time begins at the time of the index stress CMR imaging. To adjust for non-randomization of treatment, a single propensity score will be developed using logistic regression to model the decision to refer to revascularization considering all factors known to influence the referral decision. This single composite propensity score represents the probability of treatment assignment, which will be included in all subsequent survival models (step 2) associating stress CMR perfusion guided-treatment with the respective endpoints in each of the 3 sub-aims. This adjustment reduces the bias introduced by nonrandomized referral to INT in practice. While all factors known to influence this referral decision will be considered for entry into this logistic regression model, based on existing literature, the most likely predictors of referral to INT include % ischemic myocardium (% myocardial mass based on number of segments, by CMR), typical angina symptoms (yes if positive response to 2 of 3 Diamond and Forrester qualities, else no), infarct size (LGE size, grams of myocardial mass), ischemic ST changes on rest ECG (yes/no), pre-test coronary disease probability (ordinal), and prior cardiac catheterization (yes/no). We anticipate that 10-15% of patients (~n=300) received INT so model over-fitting will not occur when constructing this logistic regression model.

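### Sub-aim 2.3 judges CMR-guided INT against one published rate with no adjustment specified, so its 30% criterion could be met without a treatment effect

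*Combined protocol and SAP*

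**What the plan says.** Specific Aim 2, sub-aim 2.3, states the hypothesis that, "comparing to the FAME-2 primary outcome rate of patients managed by medical management alone", INT patients show a relative risk reduction of at least 30% in 2-year primary outcomes.

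The only statistical text for this sub-aim is the last paragraph of Sample Size. There the INT event rate "is about 5% per year, i.e. 10% in a 2-year follow-up", and the comparator is a 2-year FAME-2 rate of 19.5% in "patients who did not use physiological guidance (N=441"). With 80% power, a two-sided 5% level and a difference of 9.5 points, the plan asks for at least 180 registry patients.

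In Statistical Analyses, Step 1 of Specific aim 2 says that the propensity score enters the survival models "with the respective endpoints in each of the 3 sub-aims". The heading of that same section announces "2 separate analyses for sub-aims 2.1 and 2.2, respectively", and the Step 2 heading is also limited to 2.1 and 2.2.

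Study Endpoints defines the registry primary outcome as death, AMI and late revascularization (beyond 60 days). The first part of Sample Size gives 6% per year with ischemia and 0.5% per year without, for death and AMI only, and an ischemia prevalence of 23% (506 of 2,200).

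**The concern.** Three gaps meet in this sub-aim.

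- **No workable adjustment.** The propensity score models the choice between INT and medical therapy (MED) within the registry. The external group is known only by a percentage and a sample size, so no score can be computed for it. The promise in Step 1 cannot be kept for 2.3, and the section headings do not try to keep it.
- **Two descriptions of the comparator.** Medical management alone asks about INT versus MED. Absence of physiological guidance asks about guidance versus none. One number cannot answer both.
- **Undefined endpoints.** Sample Size does not say which events make up the 10% or the 19.5%.

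If registry patients carry lower risk than the historical arm, or if the two rates count different events, the gap will be read as a benefit of CMR-guided INT when part or all of it comes from the choice of control.

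**Working it through.** **Inputs.** From Sample Size: INT 10% at 2 years; historical 19.5%, N=441; ischemia 6% per year (death/AMI); 506 patients with ischemia. From Statistical Analyses, Specific aim 2: INT in 10-15% of 2,200, so 220-330, with about 300 named. From sub-aim 2.3: reduction of at least 30%.

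**1. The plan's own figure.** For 10% v 19.5% with the control fixed at 441, 80% power and two-sided 5%, the usual pooled two-proportion formula gives n = 154, or 172 with continuity correction. The stated 180 is not reproduced exactly. It is slightly conservative (pooled power at 180 is 85%), and nothing below depends on it. The planned reduction is 1 - 10/19.5 = 48.7%. The 30% criterion corresponds to 0.70 × 19.5% = 13.65%.

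**2. Patients with ischemia against the historical rate.** Two-year risk is 2 × 6% = 12.0% (simple) or 1 - 0.94² = 11.6% (compounded). Against 19.5%:
- 1 - 12.0/19.5 = 38.5%
- 1 - 11.64/19.5 = 40.3%

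Both exceed 30% before any INT effect is assumed.

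**3. Chance of a favourable result with no INT effect.** Suppose the true INT rate is 11.6-12.0%. The chance of significance comes from the pooled two-proportion test against 19.5% (N=441). The chance of a point reduction of at least 30% is the binomial probability of at most 24 events in 180, or 40 in 300 (13.65% of n, rounded down).

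| INT patients | P(significant v 19.5%) | P(point reduction ≥ 30%) |
|---|---|---|
| 180 | 62-67% | 75-80% |
| 300 | 78-82% | 79-84% |

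**4. A concurrent comparator from the plan's figures.** Assume that the 6% covers all 506 patients with ischemia, that every INT patient is among them, and that INT patients have 10%. The rate in the rest is (506 × r - 0.10 × n_INT) / (506 - n_INT).

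| n_INT | Rest | r = 12.0%: rate, reduction | r = 11.64%: rate, reduction |
|---|---|---|---|
| 220 | 286 | 13.5%, 26% | 12.9%, 22% |
| 300 | 206 | 14.9%, 33% | 14.0%, 29% |
| 330 | 176 | 15.8%, 37% | 14.7%, 32% |

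For example, (60.72 - 33)/176 = 15.75%, and 1 - 10/15.75 = 36.5%. The reduction of 22-37% straddles the 30% criterion.

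**5. Precision of that contrast.** Power against no difference (pooled, two-sided 5%) runs from 17% (220 v 286, 12.9%) to 48% (330 v 176, 15.75%). If the remaining patients had only 11.6-12.0%, power with 300 v 206 would be 9-11%. These figures precede any loss from matching.

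**The case against.** The strongest objection is that the rates are not like for like. A reader might infer that the plan's own figures show registry risk to be well below the historical control. They do not. The 6% counts death and AMI only, while the registry primary outcome adds late revascularization. The 6% also covers all patients with ischemia, not those treated medically, and the components of the 19.5% are not in the documents. About 7.5 extra points of events over 2 years (19.5 - 12.0) would close the gap, and the documents neither support nor exclude that. This stands, and it limits the claim to a suggestion.

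A reader might also set 10% against 12% and conclude that the true reduction is only about 17%. On the assumption that INT patients are ischemic, that denominator contains the INT patients themselves. Taking them out gives 22-37%.

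It can further be said that the plan never calls the 2.3 analysis crude, that it openly labels the comparison historical, and that sub-aim 2.1 already provides a concurrent adjusted INT v MED comparison. All of this is true. The absence of adjustment is inferred from the sample size paragraph and from silence elsewhere. Even so, 2.3 is worded as a hypothesis test of a treatment benefit, and no stated method would protect it. The reference to three sub-aims may be a slip of wording, but it leaves the reader believing in a safeguard that cannot exist.

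**Conclusion.** The point holds in this form: 2.3 rests on a comparison with one external rate, with no adjustment specified, an inconsistently described comparator and undefined endpoints. As written it cannot support a statement about the effect of CMR-guided INT. If INT had no effect and its 2-year rate were 11.6-12.0%, the plan would still give a significant result with 62-82% probability and a point reduction of at least 30% with 75-84% probability (180 to 300 patients). Against the remaining ischemic patients, the assumed INT rate implies a reduction of about 22-37% rather than 49%.

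These sizes rest on the 6% being a usable stand-in for 2-year registry risk on the relevant endpoint. The 22-37% also assumes that all INT patients are ischemic, that they are included in the 6%, and that the 10% counts the same events. The documents confirm none of these.

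A reader might infer that the formal 30% test should simply move to an internal control. The plan's figures do not support that: power is about 9-48% even against no difference, and showing a reduction beyond 30% would be harder still.

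**What to change.** 1. Give the 2.3 comparator one description in both Specific Aim 2 and Sample Size.
2. Use the registry's primary-outcome definition at 2 years for 2.3, state which events the 10% and the 19.5% count, and report any mismatch with the historical endpoint.
3. Report 2.3 as a descriptive benchmark: the INT rate with its confidence interval beside the published rate, with a sentence saying that it does not support a treatment-effect claim.
4. Rest any statement about the effect of CMR-guided INT on the concurrent propensity-adjusted INT v MED comparison of sub-aim 2.1. Add a 2-year estimate with confidence interval among patients with ischemia, without a formal test of the 30% threshold.
5. In Step 1, limit the scope of the propensity score to sub-aims 2.1 and 2.2.

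The cost is SAP wording and one further estimate from data already planned for collection. The downside is real: the formal 2.3 claim is lost, and the concurrent estimate will probably be less favourable and imprecise.

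### Sub-aim 2.3 claims a relative risk reduction of at least 30%, but 180 patients at 80% power fits only a test of no difference; power for the claim itself is about 25–29% at 180 and 35–45% at 300

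*Combined protocol and SAP*

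**What the plan says.** Specific Aim 2, Sub-aim 2.3, takes the FAME-2 medical-management rate as comparator and says the study will test that "CMR-guided INT patients have a relative risk reduction of 2-year primary outcomes" of 30% or more.

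The Sample Size section, in its paragraph on sub-aim 2.3, gives the planning figures:

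- The event rate after CMR-guided revascularization "is about 5% per year, i.e. 10% in a 2-year follow-up".
- For the comparator, "the 2-year event rate of patients who did not use physiological guidance (N=441), was 19.5"%.
- With 80% power and a two-sided 5% level, the conclusion is "an assumed difference under H1 of -9.5%, the sample size of patients in this registry needs to be at least 180 patients".

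The 30% threshold does not enter this calculation, and no null value is stated.

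In Statistical Analyses, the heading for Specific aim 2 announces "2 separate analyses for sub-aims 2.1 and 2.2, respectively", and Step 2 names the same two sub-aims. Step 1 gives the number of INT patients to expect: "We anticipate that 10-15% of patients (~n=300) received INT".

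**The concern.** A hypothesis of an RRR of at least 30% puts the boundary at 13.65%, which is only 3.65 points above the assumed 10%. The calculation uses the whole 9.5-point distance to 19.5%. The 80% power is therefore attached to a different and much easier question than the one the sub-aim asks.

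Rejecting no difference shows that the INT rate is below the historical rate. It does not show that it is lower by 30% or more. With no decision rule in the document, nothing stops a merely significant result from being reported as support for the 30% figure. The protocol's rationale says the aims should supply core evidence for reimbursement decisions, so an unsupported effect-size claim would matter.

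**Working it through.** **Inputs.** INT rate p1 = 0.10; historical rate p0 = 0.195 with n0 = 441; two-sided 5% (z = 1.96); 80% power; minimum n = 180 (all from Sample Size, sub-aim 2.3). Threshold RR = 0.70 (Sub-aim 2.3). Expected INT patients: 10–15% of 2,200 = 220–330, given as about 300 (Step 1). The assumed true RRR is 1 − 0.10/0.195 = 48.7%.

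**1. The plan's own figure.** Test of no difference, pooled variance:

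power = Φ{[(p0 − p1) − 1.96·√(p̄(1−p̄)(1/n + 1/n0))] / √(p1(1−p1)/n + p0(1−p0)/n0)}

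At n = 180, p̄ = (18 + 86)/621 = 0.1675. This gives (0.095 − 1.96 × 0.0330)/0.0293 = 1.03, so power is 85.0%; with continuity correction it is 81.6%. The n for 80% power is 154 (pooled) or 172 (continuity corrected). The 180 is not reproduced exactly, but it is slightly conservative and adequate for this test.

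**2. Power to show RRR above 30%,** with the true rates as planned, by three tests:

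- *Log-RR:* Φ{[ln 0.70 − ln(0.10/0.195)]/SE − 1.96}, SE = √(0.9/(0.1n) + 0.805/(0.195 × 441)). At 180: 0.311/0.2436 − 1.96 = −0.68, so 24.7%. At 300: 0.311/0.1984 − 1.96 = −0.39, so 34.8%.
- *Linear contrast p1 − 0.7·p0:* Φ{0.0365/√(0.09/n + 0.49 × 0.157/441) − 1.96}. At 180: 0.0365/0.0260 − 1.96 = −0.55, so 29.0%. At 300: 0.0365/0.0218 − 1.96 = −0.28, so 38.8%.
- *13.65% taken as a known constant:* Φ{[0.0365 − 1.96·√(0.1365 × 0.8635/n)]/√(0.09/n)}. At 180: −0.61, so 27.1%. At 300: −0.14, so 44.6%.

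| INT patients | log-RR | linear contrast | fixed 13.65% |
|---|---|---|---|
| 180 | 24.7% | 29.0% | 27.1% |
| 220 | 28.4% | 32.7% | 33.1% |
| 300 | 34.8% | 38.8% | 44.6% |
| 330 | 36.9% | 40.8% | 48.7% |

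A simulation of 400,000 runs gives, in the same order, 22%, 32% and 28% at 180, and 34%, 40% and 47% at 300. No single n gives 80%. It takes about 645 if 19.5% is treated as known and about 3,030 by log-RR. The linear contrast never gets there (ceiling 78.9%), because the 441 historical patients are fixed.

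**3. The other natural reading: 30% as the smallest effect to detect against no difference.** Put p1 = 0.1365 in the formula of step 1. Power is 40.3% at 180 and 54.7% at 300.

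**4. What a significant no-difference test would establish.** Take 86/441 = 19.5% for the comparator. At 300 INT patients, significance is reached with 41 events (13.7%). Then RR = 0.701, SE(ln RR) = √(1/41 − 1/300 + 1/86 − 1/441) = 0.174, and the RRR is 30% with a 95% CI of about 1% to 50%. If the true RRR is only 20–25%, so that the 30% claim is false, this test is still significant 20–29% of the time at 180, 27–40% at 300 and 29–42% at 330.

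**5. What the 30% claim requires.** For the lower 95% limit of the RRR (log-RR) to reach 30%:

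- At 300, at most 27 may have an event (9.0%, observed RRR 54%) when 30 are expected.
- At 180, at most 14 (7.8%, observed RRR 60%) when 18 are expected.

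At exactly the planned rates the 95% CI for the RRR would be 17% to 68% at 180 and 24% to 65% at 300, so both intervals include values below 30%.

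**The case against.** The strongest reply is that low power follows only if a confidence limit must exclude an RRR below 30%, and no section says that. Two softer rules would fit 180 patients well. If the observed RRR need only reach 30%, the chance is about 92% at 180 and 95% at 300. If the no-difference test must also be significant, it is about 85% at 180 and 95% at 300. At 180, significance needs at most 23 events, which is already an observed RRR of 34%.

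It is true that the document states no rule. But neither softer rule is written anywhere, and neither shows that the true reduction is at least 30%. The joint rule is still met 20–29% of the time at 180, and 21–34% at 300, when the true RRR is 20–25%. At 180 it is in effect the no-difference test under another name.

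Other points on that side:

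- *Large-sample formulas with only 18–30 expected events are approximate.* Agreed. Simulation widens the ranges to 22–32% at 180 and 34–47% at 300, which leaves the conclusion unchanged.
- *A one-sided 5% test would do better.* Power would be at most 41% at 180 and 59% at 300, and the plan specifies two-sided.
- *Step 1 refers to three sub-aims, so 2.3 is covered.* It says only that the propensity score will enter the Step 2 survival models, and Step 2 is limited to 2.1 and 2.2. That score models INT versus medical referral within the registry and defines no comparison with a historical 19.5%.
- *The arithmetic behind 180 is sound, and this is one sub-aim of an observational registry.* Both are true. The fault is that the calculation answers a different hypothesis.

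**Conclusion.** The concern holds. The stated 80% power does not belong to the stated hypothesis. On the plan's own rates (10% against 19.5%, 441 historical patients, two-sided 5%), power to show an RRR above 30% is about 25–29% at the 180 minimum, about 35–45% at 300, and 28–49% over the expected 220–330. The spread reflects the choice of test and whether the historical rate is treated as known without error.

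These figures read the hypothesis as something the data must demonstrate at the stated error rate. Treating 30% as the smallest detectable effect does not restore 80% either. The problem is confined to sub-aim 2.3 and does not touch the 2,200 set for Aim 1.

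**What to change.** Choose one of the following and write it in both Specific Aim 2 and Sample Size.

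- **(a)** Restate sub-aim 2.3 as a lower 2-year risk than the historical 19.5%, with a null of no difference. Keep 180 as its minimum size. Report the RRR with its 95% CI and make no claim of 30% or more.
- **(b)** Keep the 30% hypothesis and declare it met only if the lower 95% confidence limit of the RRR is at least 30%. State whether the sampling error of the 441 historical patients is counted. Replace the 80% with the power of the chosen test (about 25–29% at 180, about 35–45% at 300).

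In either case, add the null hypothesis, test and interval for 2.3 to Statistical Analyses, which now specifies only 2.1 and 2.2.

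The cost is rewording, with no extra patients or data. The price is a weaker claim under (a) or a less favourable power statement under (b).
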